**9. HANDLING OF MISSING AND INCOMPLETE DATA**

It is required that data be entered into the secure online database, Joint Assist. A review of data will be made at the beginning of each month to monitor the completeness of each required milestone. Missing or incomplete data will not be reimbursed. It is imperative that all required data is collected at the appropriate time window and entered in to Joint Assist in a timely manner. Data reimbursement will not begin until a complete enrollment (preop, operative and 0-12 week visit) is entered into Joint Assist. If a patient misses a visit, and refuses to return for a clinical exam, a "Phone Follow-up KSS," and "PROMS Questionnaire" case report form can be completed at the discounted rate (if applicable) defined in the investigator agreement. If that event occurs, the Knee Society objective score would not be collected.

**10. DATA COLLECTION, HANDLING AND RETENTION****10.1. SOURCE DOCUMENTATION REQUIREMENTS**

A. Source documentation for this study will be maintained to document the treatment and study course of a subject and to substantiate the integrity of the trial. Source documentation will include, but not be limited to, paper or electronic case report forms, hospital and/or clinic or office records documenting subject visits including study and other treatments or procedures, medical history and physical examination information, laboratory and special assessments results, radiographic images, pharmacy records, and medical consultations (as applicable).

**10.2. CASE REPORT FORMS**

A. Data for this clinical trial will be collected and documented on the subject Case Report Forms (CRFs) provided which may be in paper form or in an electronic form. The paper case

report forms match the electronic case report forms. The paper case report forms can be used as an example of the electronic case report forms in the event the IRB requires review of CRFs.

Authorized study site personnel will complete CRFs only. CRFs must be reviewed and signed by the Investigator or his/her designees as applicable or required by the CRF. Electronic CRFs, via the online database Joint Assist, will utilize user-authentication via user name and password, to apply electronic signature to CRFs. Any data entered to the database is managed with an audit trail that will record the user name of all those entering and / or changing data in this study.

**10.3. ELECTRONIC DATA ENTRY (where appropriate)**

A. When using electronic trial data handling and/or remote electronic trial data systems, the sponsor will:

1. Ensure and document that the electronic data processing system(s) conforms to the sponsor's established requirements for completeness, accuracy, reliability, and consistent intended performance (i.e. validation).
2. Maintains SOPs for using these systems.
3. Ensure that the systems are designed to permit data changes in such a way that the data changes are documented and that there is no deletion of entered data (i.e. maintain an audit trail, data trail, edit trail).
4. Maintain a security system that prevents unauthorized access to the data.
5. Maintain a list of the individuals who are authorized to make data changes.
6. Maintain adequate backup of the data.

**11. DATA REPORTING****11.1. ANNUAL REPORT**

A. Once all centers are enrolled, and data is available, an annual report will be written by the sponsor for purposes of IRB renewal. Data included in this report will be general demographics, adverse events, revisions / reoperations, subject withdrawals, and protocol deviations. The report will summarize data for the entire study. Site level reports and specific data queries are available upon request.

**11.2. FINAL REPORT**

- A. Once the study is complete, a final report will be documented with primary and secondary endpoint analysis. This report will be distributed to all participating centers within 6 months of completion of the study.

**12. RISK ANALYSIS**

Please reference the risk analysis provided in the package insert for each device that is available as a part of the investigator binder.

**13. MONITORING PLAN**

Monitoring is not required for post-market studies, however, Biomet, as the sponsor of this study, may monitor the data collection to ensure that the investigation is being conducted consistent with the protocol. A pre-investigational visit or training webinar is required for all sites, and routine monitoring (onsite or in-house) of the quality of the data will be completed at minimum, annually.

**13.1. PRE INVESTIGATIONAL SITE VISIT:**

- A. Prior to initiation of the study, the study manager will provide the Investigator with all the necessary information to enable him to carry out his responsibilities. This prepares the site with an in-depth training on the protocol, case report forms, and data collection process for the length of the study. The study manager or designee will also train the site on using the Biomet Joint Assist database. This visit may be done by physical visit to the site, or training via webinar.

**13.2. STUDY CLOSE-OUT**

- A. At the end of the study, an effort to resolve all pending data queries will be completed to ensure the integrity of the data for final data analysis.

**14. ETHICAL AND REGULATORY REQUIREMENTS****14.1. CODE OF CONDUCT**

- A. The Investigator will ensure that the clinical study is conducted in accordance with
  1. Protocol
  2. Regulatory and IRB/EC requirements

**14.2. REGULATORY APPROVAL**

- A. The devices being studied are post-market non-investigational devices cleared by the FDA via 510(k) regulatory pathway. The Vanguard CR Knee System was originally cleared as a part of 510(k) K023546 and was called the “Maxim Accel” Knee, later branded as “The Vanguard Total Knee System” in January of 2003. The Vanguard XP Knee system was cleared via 510(k) K122160 in March of 2013. The patients included in this study would receive knee replacement without participating in the study. This study is as a post market surveillance study for purposes of better understanding implant performance and patient perceived assessment of their recovery.

**14.3. INSTITUTIONAL REVIEW BOARDS/ETHICS COMMITTEE**

- A. The Investigator must obtain appropriate Institutional Review Board (IRB) approval before the study can be initiated. The investigator should assess if there are any local IRB requirements, and either gain approval through local IRB, or through a commercial IRB. A copy of the written approval from the IRB and a copy of the approved informed consent form should be sent to the Sponsor.
- B. Any changes to the protocol must be discussed and approved by the Sponsor in writing unless the change is made to assure the safety of the subject. In the non-emergent setting, after agreement on the changes has been reached, an amendment to the protocol will be provided by the Sponsor for submission to the IRB for review and approval prior to initiation of the change. Any change made emergently must be documented in the subject's medical record and reported to the Sponsor within the time period required by local SOPs and applicable regulations.
- C. The Investigator must immediately forward to the IRB any written safety reports or updates from the Sponsor. The Investigator must keep the IRB informed of the progress of the study as required by the IEC but at least annually.

**14.4. INFORMED CONSENT**

- A. All patients require informed consent due to the research interventions and data collection required of this study. Subjects (or the subject's legally authorized representative) will be provided with an informed consent in order to give ample opportunity to review the consent and ask questions. The signed informed consent will be obtained before any study procedures begin. If the subject agrees to participate in the study, the

subject/representative must sign the informed consent form. The Investigator or his/her qualified designee must also sign the informed consent form. A copy of the informed consent form should be given to the subject/representative. All subjects who meet all of the entry criteria will be considered for inclusion in this trial. Any subject meeting any of the exclusion criteria will be excluded from the trial.

- B. The informed consent form must be approved by the institution's IEC/IRB.
- C. Subjects will be informed of new information learned during the study, which may affect the subject's decision to continue participation in the study.
- D. An enrollment case report form will document for the sponsor that the center has obtained the required signed informed consent form. Fully signed informed consent forms (or copies) are to be maintained in the study file by all centers, and must be available for verification by monitors or inspectors.

**14.5. SUBJECT CONFIDENTIALITY**

- A. General Responsibilities:
  - 1. The Sponsor and centers will maintain the confidentiality of the identity of subjects enrolled in the study and the information contained in their study records. The Sponsor will also instruct the study investigators in the importance of maintaining the confidentiality of study records. The records will be made available as required for review by governing regulatory agency such as FDA and a reviewing IEC/IRB, however to the extent possible, the subject's identity will not be disclosed.
- B. Electronic Data Capture
  - 1. Once the site enters a patient into Joint Assist, the database will assign that patient an ID number. It is the responsibility of the investigator to maintain a list of patient identification and Joint Assist ID numbers throughout the course of the study. By assigning patients a unique ID number, their identity is protected in Joint Assist, the online database. The database is restricted, allowing a doctor to only view and enter data from his own patients. User authentication is required to view research data. The data is transmitted to a centralized database through a secured (SSL) channel on the Internet. Data in transit is in 128-bit encryption. The access to the centralized database is limited to those who are responsible for maintaining the database.

**15. STUDY DEFINITIONS**

- A. **Revision:** A procedure that removes part of the original implant configuration, with or without replacement of the entire component configuration.
- B. **Removal:** A procedure where all of the original system configuration is removed.
- C. **Reoperation:** Any surgical procedure that does not include removal or revision, for example, drainage of a hematoma at the surgical site.
- D. **Adverse Events:** Adverse events will be documented according to ISO 14155:2011 definitions as follows. Since this is not an investigational medical device study (post market study), "investigational" has been removed from the definition. For the purposes of this study, only adverse events meeting the following criteria will be included, unless otherwise reported at the discretion of the investigator:

- E. **Serious Adverse Event (SAE):** adverse event that:
  1. led to death,
  2. led to serious deterioration in the health of the subject , that either resulted in
  3. a life-threatening illness or injury, or
  4. a permanent impairment of a body structure or a body function, or
  5. in-patient or prolonged hospitalization, or
  6. medical or surgical intervention to prevent life-threatening illness or injury or permanent impairment to a body structure or body function,
  7. led to fetal distress, fetal death, or a congenital abnormality or birth defect

*NOTE: Planned hospitalization for a pre-existing condition, or a procedure required by the CIP, without serious deterioration in health is not considered a serious adverse event.*

- F. **Adverse Device Effect (ADE):** adverse event related to the use of a medical device; this includes adverse events resulting from insufficient or inadequate instructions for use, deployment, implantation, installation, or operation, or any malfunction of the medical device; includes any event resulting from user error or from intentional misuse of the medical device.
- G. **Serious Adverse Device Effect (SADE):** adverse device effect that has resulted in any of the consequences characteristic of a serious adverse event.

H. **Unanticipated Serious Adverse Device Effect (USADE):** serious adverse device effect which by its nature, incidence, severity or outcome has not been identified in the current version of the risk analysis report.

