**2.5. PRIMARY AND SECONDARY ENDPOINTS**

- A. Primary Endpoint: Percentage of patients reporting their knee feels “normal”.
- B. Secondary Endpoints: Patient Reported Outcome Measures “PROMs”, Knee Society Score, Complication Rate, Pain Relief, Functional outcomes, Survivorship

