## 2.6. ASSESSMENT PROCEDURE

**Table 2.6-A**

Form	Pre-op (screening)	Operative (Enrollment)	Discharge	3 Mos	6 Mos	1 Yr	2 Yrs	3 Yrs	5 Yrs	7 Yrs	10 Yrs
Screening Log	X										
Informed Consent	X										
Demographics / Medical History	X										
Operative Form		X									
Modified Knee Society Score*	X		X	E†	SC***	X	X				
PROMS** Questionnaire	X		X	E†	SC***	X	X	X	X	X	X
Radiographs: AP, ML, Skyline			X	E†	SC***	X	X				
Radiographic Form			X			X	X				
Adverse Events		AS NEEDED	AS NEEDED	AS NEEDED	AS NEEDED	AS NEEDED	AS NEEDED	AS NEEDED	AS NEEDED	AS NEEDED	AS NEEDED
Withdrawals		AS NEEDED	AS NEEDED	AS NEEDED	AS NEEDED	AS NEEDED	AS NEEDED	AS NEEDED	AS NEEDED	AS NEEDED	AS NEEDED
Protocol Deviations		AS NEEDED	AS NEEDED	AS NEEDED	AS NEEDED	AS NEEDED	AS NEEDED	AS NEEDED	AS NEEDED	AS NEEDED	AS NEEDED

\*Modified Knee Society Score includes an additional assessment of incidence of anterior knee pain. This additional question is exploratory and will not affect the total score of the KSS. In the event that a patient does not return for a visit, a partial “Phone Knee Society Score” can be completed and entered into the database.

\*\*Patient Administered Outcome Scores “PROMS” Questionnaire can be collected in the office, over the phone, or via mailer. The questionnaire contains SANE/Patient Satisfaction, Oxford Knee Score, EQ-5D, KOOS, and the Forgotten Joint Score validated patient administered outcomes scores. These scores are combined into the paper version for easier administration to patients for completing. When entering to Joint Assist, these scores will be separated but contain the same exact questions.

\*\*\*SC: 6 Month visit should be collected only if standard of care. Radiographs should be taken if standard of care at the center, however no radiographic form will be collected. Any adverse event or failure determined from radiographs should be documented on an adverse event form. All visits will be documented relative to the clinical site in the approved informed consent.

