**G. Safety**

1. Adverse Events: Please reference section **6**, and section **15** for Adverse event data collection method and definitions. Only serious and device related adverse events will be collected for this study. Patient hospital readmissions should be documented on an adverse event form, and the relation to the device documented.
2. Revisions / Removals: Please reference section **4** and section **15** for Revision / Removal data collection method and definitions.
3. Withdrawals: Please reference section **3.4** for detailed data collection methods, and section **15** for relative definitions.
4. Protocol Deviations: Please reference section **5** for Protocol Deviation data collection methods for this study.

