**H. Radiographic Assessments (including Radiographic Assessment protocol)**

1. Views
  - a. Standard Anterior-Posterior (AP)
  - b. Standard Lateral View

- c. Skyline merchant's view
- d. Standing alignment (Long leg)

2. Placement

- a. The X-ray should show the total prosthesis including the entire length of the femoral and tibial stem.

3. Radiographic Collection Periods

- a. 0 to 12 weeks postoperative as baseline
  - i. Standing Long Leg AP
  - ii. Standard Short Films (AP, ML, Skyline)
- b. 1 Year Follow-up
  - i. Standard Short Films (AP, ML, Skyline)
- c. 2 Year Follow-up
  - i. Standard Short Films (AP, ML, Skyline)

4. Radiographic Assessment Form

A radiographic assessment form will document the radiographic findings for each patient in this study. The 0-12 week films are to be used as baseline radiographic data for subsequent follow-up assessments / comparisons at 1 and 2 years post-op.

- a. Standing AP Long Leg Film: A standing long leg x-ray will be taken at 0-12 weeks in addition to standard films in order to document mechanical leg alignment.
- b. Standard Short Films:
  - i. Assessments will be done according to the Knee Society Total Knee Arthroplasty Roentgenographic Evaluation for:
    - 1. Alignment of components - (Standard Films)
    - 2. Radiolucent lines (RLL) - (Standard Films)
  - ii. Migration/Subsidence – (Standard Films)
- c. If any osteolysis (a radiolucent line greater than 2mm in two or more zones that was not present on the 0-12 week x-ray) or gross shifting or migration of components (movement greater than 3mm or greater than 3 degrees as compared to the 0-12 week x-ray) is noted, it should be documented on a adverse event form.

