**3.4. SUBJECT WITHDRAWAL****A. Voluntary Participation:**

It is recognized that the subject's participation in this trial is entirely voluntary, and that she/he may refuse to participate and may withdraw from participation at any time without jeopardy to any future medical care. It is also recognized that the investigator, at his/her discretion, may withdraw a subject from this study based upon his/her professional judgment. In event of subject withdrawal, applicable local procedures should be followed. Patients who are withdrawn from the study will not be replaced, and a Withdrawal form should be completed.

**B. Withdrawals:** All subject withdrawals must be documented on the Withdrawal Form. If withdrawal is due to patient death, or removal of components as indicated below, a withdrawal form should be completed. If the patient is withdrawn after receiving the randomized treatment, the subject will NOT be replaced.

**C.** If a patient receives a partial revision (patella or polyethylene replacement), or a reoperation (e.g.: manipulation), this should be documented on an adverse event form and the patient should continue to be followed in the study.

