### **6. ADVERSE EVENT MANAGEMENT AND REPORTING**

A record of all device related and serious adverse events, including details of the nature, onset, duration, severity, relationship to the device, relationship to the operative procedure and outcome, will be made on the relevant section(s) of the Adverse Event Form. The subject should be questioned about progress with previously reported adverse event(s) at each subsequent follow-up assessment visit. Definitions to be used for adverse event reporting are included in section 15. Any serious or unanticipated adverse events should be reported to the sponsor as soon as possible, as it is required to report unanticipated adverse events to the FDA within 10 days of knowledge of the event.

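### Apart from a list of always-recorded events, a non-serious knee complication is recorded only if an investigator with no described blinding calls it device-related or chooses to report it, so the between-arm complication rate can reflect reporting

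*Combined protocol and SAP*

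**What the plan says.** Section 2.5 lists the secondary endpoints, among them "Knee Society Score, Complication Rate, Pain Relief, Functional outcomes, Survivorship". No section gives Complication Rate an event list, a time window or a data source. Section 8.3 compares categorical safety and secondary outcomes between arms by the likelihood ratio chi-square test, or Fisher's exact test for small tables.

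The collection rule appears three times:
- Section 2.7 G: "Only serious and device related adverse events will be collected for this study".
- Section 6 asks for "A record of all device related and serious adverse events".
- Section 15 D: "only adverse events meeting the following criteria will be included, unless otherwise reported at the discretion of the investigator".

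Some events are recorded without a relatedness condition:
- Readmissions (Section 2.7 G): "Patient hospital readmissions should be documented on an adverse event form, and the relation to the device documented".
- Partial revisions (Section 3.4 C), "or a reoperation (e.g.: manipulation), this should be documented on an adverse event form". Section 4 also sends partial and full revisions to that form.
- Osteolysis over a stated threshold, or "gross shifting or migration of components (movement greater than 3mm or greater than 3 degrees as compared to the 0-12 week x-ray" (Section 2.7 H).
- Radiographic events more generally, in the six-month footnote to Table 2.6-A: "Any adverse event or failure determined from radiographs should be documented on an adverse event form".
- Intraoperative complications, which go on the operative record (Section 2.7 E).

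On blinding, Section 2.4 covers the patient only, and only until surgery. No blinded assessor or adjudication of events is described.

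**The concern.** Outside the always-recorded events, whether a non-serious knee event exists in the data depends on someone who knows the implant. Examples are an effusion, a superficial wound problem, instability symptoms, or stiffness managed without a procedure. Such an event enters only if the investigator attributes it to the device or decides to report it anyway.

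Randomisation makes the arms comparable for the events that occur. It does not make them comparable for the events that are recorded when recording rests on an implant-aware judgement. If that judgement differs between XP and CR, a difference in the recorded rate, or its absence, cannot be read as a difference in complications.

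**Working it through.** **1. The plan's own figures.** The documents give no figure for the complication rate, so there is none to reproduce. The number per arm comes from Section 8.1: 66% versus 83%, two-sided alpha 0.05 and 90% power give 137 per group (power at 137 is 0.902). Dividing by 0.90 gives 152.2, rounded up to 153. Both figures reproduce.

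**2. Which events depend on the investigator's call.**

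| Event | Route into the data | Depends on attribution or choice? |
|---|---|---|
| Intraoperative complication | Operative record (2.7 E) | No |
| Serious event, readmission | Adverse event form (2.7 G, 6) | No |
| Revision, reoperation, manipulation | Adverse event form (3.4 C, 4) | No |
| Threshold osteolysis or migration; radiographic event | Adverse event form (2.7 H; Table 2.6-A footnote) | No |
| Any other non-serious knee event | Adverse event form only if device-related or volunteered (2.7 G, 6, 15 D) | Yes |

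**3. Illustration of size.** Every rate here is assumed, because the documents give none. Let s be the share of knees with an always-recorded event, q the true share with another non-serious knee event, and r the share of those reported. Set s and q equal in both arms and let only r differ. With the two kinds of event independent, the recorded rate is

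p = s + (1 − s) × q × r.

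With s = 5% and q = 20%:
- r = 50%: p = 0.05 + 0.95 × 0.20 × 0.50 = 14.5%
- r = 25%: p = 0.05 + 0.95 × 0.20 × 0.25 = 9.75%
- r = 40%: p = 0.05 + 0.95 × 0.20 × 0.40 = 12.6%
- r = 30%: p = 0.05 + 0.95 × 0.20 × 0.30 = 10.7%

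The chance of p < 0.05 was found by enumerating two independent binomials of 153 knees with the likelihood ratio test. Alpha of 0.05 is assumed, since none is stated for secondary outcomes, and knees are treated as independent.

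| q (s = 5%) | 50% vs 25% reported | 40% vs 30% reported | Equal (50% vs 50%) |
|---|---|---|---|
| 10% | 12% | 6.5% | 5% |
| 20% | 25% | 8% | 5% |
| 30% | 41% | 11% | 5% |

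Check by normal approximation at q = 20%:
- 14.5% vs 9.75%: SE = sqrt((0.145 × 0.855 + 0.0975 × 0.9025)/153) = 0.0372; z = 0.0475/0.0372 = 1.28; rejection about 0.25.
- 12.6% vs 10.7%: SE = sqrt((0.126 × 0.874 + 0.107 × 0.893)/153) = 0.0367; z = 0.019/0.0367 = 0.52; rejection about 0.08.

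**4. Effect of the always-recorded events.** With s = 0 and q = 20%, the recorded rates would be 10% vs 5% and 8% vs 6%, and the rejection rates 40% and 11%. The always-recorded events dilute the contrast, so these larger figures overstate it.

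**The case against.** The strongest reply is that light collection is a consistent and deliberate choice: Sections 2.7 G, 6 and 15 agree, and Section 14.2 describes a post-market study of two cleared devices. That is a fair reason for not collecting every non-knee event. It does not help a randomised comparison of knee complications.

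Several stronger readings are tempting, and the documents do not support them:
- A reader might infer that every non-serious event depends on the investigator's call. It does not, as the table shows. A stiff knee that undergoes manipulation is recorded in either arm.
- A reader might take device-related to mean implant fault. Section 15 F is broader: it includes events arising from implantation, inadequate instructions and user error. This narrows the gap but still requires a judgement.
- A reader might infer that XP, as the newer device, would attract more attributions. Section 1.1 calls CR established but also describes early XP experience favourably, so the direction is open. Differential reporting itself is possible, not shown.
- A reader might take it as settled that the endpoint is computed from adverse event forms. No section says so. It is an inference from the absence of any other general post-operative source, and a definition restricted to serious or always-recorded events would largely avoid the problem.
- A reader might conclude that unreported events are lost for good. Section 10.1 retains clinic and hospital records, so some could be recovered, though not reliably or evenly.

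It is also true that deleting the discretion clause alone would cure little. An unblinded investigator would still decide what counts as an event.

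**Conclusion.** The concern holds in a limited form. For non-serious knee events outside the always-recorded group, the stated rule lets an implant-aware judgement decide what enters the data. If the undefined Complication Rate draws on the adverse event form, it can differ between arms with no true difference, in either direction.

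Under the assumed 20% and 5% event rates, the false-positive rate would be about 25% for a two-fold reporting gap and about 8% for a modest one, against about 5% with equal reporting. Varying the non-serious rate from 10% to 30% gives 6.5% to 41% across these two gaps. These figures illustrate the mechanism and are not estimates for this trial. The point affects one secondary endpoint and leaves the primary analysis untouched, so the change is advisable rather than essential.

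**What to change.** - In Sections 2.7 G, 6 and 15 D, prespecify a list of index-knee complications (for example effusion, stiffness, superficial wound problem, instability symptoms), each with a short definition. Record them in both arms at existing visits, regardless of seriousness or device attribution. Keep relatedness as a descriptor.
- In Section 2.5, define Complication Rate as the listed events plus serious events, readmissions, revisions, reoperations, threshold radiographic findings and intraoperative complications. State the time window.
- Do not count discretionary reports in that endpoint; they can be tabulated separately.
- Keep the serious-or-device-related rule for non-knee events.

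The cost is a protocol amendment, modest extra data entry and a higher stated complication rate in both arms. Some reporting bias will remain without blinded assessment, because the investigator still judges whether a listed event is present.
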